8.4.2 Concomitant Medications

The number and percent of patients receiving concomitant medications or treatments prior to and during the study and at the final visit will be tabulated and presented overall and by treatment group for the Safety analysis dataset. Concomitant medications and treatments will be summarized using descriptive statistics and will be presented by type of drug (Anatomical Therapeutic Chemical Classification [ATC] level 1) by treatment group.

8.4.3 Clinical Laboratory Tests

Hematology and chemistry data will be listed for each subject. Values outside the normal laboratory reference range will be flagged as high or low on the listings. Summaries over time and changes from baseline over time will be provided. Depending on the size and scope of the changes, shift tables showing baseline to post-baseline categorization that are below, within, and above normal range may be provided.

8.4.4 Vital Signs

Vital signs will be listed for each subject. These will include temperature, respiration, pulse, and blood pressure. Summaries over time and changes from baseline will be provided.

8.5 Efficacy Analyses

The efficacy analysis of the endpoints are detailed in Section 3.2 and 3.2 above.

8.6 Multiplicity Adjustment

The secondary analyses are considered supportive to the primary analysis. In order ensure the appropriate alpha level for all tests (without a multiplicity adjustment) a hierachial testing scheme will be employed in the order specified in Section 3.2.

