Vital signs will be collected daily during the treatment period and at follow-up visits from medical records as follows: heart rate (or pulse rate), systolic BP, diastolic BP, body temperature (°F in the US, °C out of the US), respiratory rate. Vital signs are collected shortly after (within 30 minutes) treatment.

Hematology

Hematology lab tests will be collected from the medical records at baseline and every other day through treatment and hospital stay (as applicable) unless an abnormal value is observed. In the case of an abnormal lab result, continue to collect and test those samples to follow subject through resolution.

The following hematology labs are tested: white cell count, red blood cell count, hemoglobin, hematocrit, mean cell volume (MCV), mean cell hemoglobin (MCH), mean cell hemoglobin concentration (MCHC), platelets, neutrophils, lymphocytes, monocytes, eosinophils, and basophils.

Serum Biochemistry

Biochemistry lab tests will be collected from the medical records at baseline and every other day through treatment and hospital stay (as applicable) unless an abnormal value is observed. In the case of an abnormal lab result, continue to collect and test those samples to follow subject through resolution.

The following biochemistry lab tests are tested: sodium, potassium, chloride, bicarbonate, urea, creatinine, glucose, total calcium, phosphate, ferritin, high-sensitivity C-reactive protein (hs-CRP), protein, albumin, globulins, total bilirubin, alkaline phosphatase (ALP), alanine aminotransferase (ALT), aspartate aminotransferase (AST) and lactate dehydrogenase (LDH).

Cytokine and Chemokine Assays

Cytokine and chemokine assay lab test results will be collected and recorded before and after treatment (at baseline and again at Day 5 and at hospital discharge). A cytokine panel is tested to include, but not limited to: Tumor Necrosis Factor alpha (TNF α), interferon gamma (IFN γ), Interleukin 1 beta (IL-1 β), interleukins (IL-6, IL-8, IL-10, IL-12). Data is reported for research purposes, and the sample is destroyed after data is collected.

Ordinal Scale for Clinical Improvement

The clinical status will be recorded at every visit from baseline to Day 60 using the World Health Organization (WHO) “Ordinal Scale for Clinical Improvement”. This 8-point ordinal

scale was created to be responsive to the eligible patient population, intervention, and course of illness of COVID-19. The following is scores are collected:

Score	Descriptor

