9.4.2 Secondary Endpoints

Secondary efficacy endpoints assess the effect of IV Ampion compared to SOC on the clinical outcomes for participants with COVID-19 on supplemental oxygen. The secondary endpoints will be tested in a hierarchical manner in the order presented, and thus no adjustment to the alpha level is necessary:

Objective	Endpoint
Secondary Endpoints	
Assess the effect of Ampion compared to placebo on safety	
Incidence of adverse events (AEs) and serious adverse events (SAEs) from baseline to Day 60.
Assess the effect of Ampion compared to placebo on clinical improvement	
Change in ordinal scale from baseline through Day 7.Change in ordinal scale from baseline to hospital discharge or day 14 (whichever occurs first).Change in ordinal scale from baseline to hospital discharge or day 28 (whichever occurs first).Change in NEWS2 score from baseline through Day 5.Change in NEWS2 score from baseline to hospital discharge.Modulation of cytokine levels from baseline to Day 5.
Assess the effect of Ampion compared to placebo on duration of respiratory failure to ventilator-free days.	
Percentage of participants who progress to respiratory failure (i.e., need for mechanical ventilation, ECMO, non-invasive ventilation) by Day 28.

Objective	Endpoint
Assess the effect of Ampion compared to placebo on intensive care	
Percentage of participants who require Intensive Care Unit (ICU) admission by Day 28.ICU-free days through Day 28.ICU LOS from ICU admission to discharge.
Assess the effect of Ampion compared to placebo on hospital stay	
Hospital length of stay (LOS) from admission to discharge.Hospital-free days through Day 28.
Assess the effect of Ampion compared to placebo on oxygen use	
Duration of oxygen use, blood oxygen saturation, and oxygen flow rate from baseline through Day 5.

The efficacy endpoints will be evaluated to estimate the treatment effect and use descriptive statistics including mean, standard deviation, percentages, minimum/maximum, and 95% confidence intervals. All endpoints will be tabulated and presented by treatment arm, cohort (severe and critical), and timepoint. Where appropriate, data will be tabulated and presented cumulatively across cohorts and/or timepoints.

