3.2 Secondary Endpoints

3.2.1 Change in ordinal scale from baseline through Day 7, Day 14 and Day 28.

The hypotheses to be tested are:

$$H_0: \mu_A = \mu_S \text{ versus } H_A: \mu_A \neq \mu_S$$

Where μ_A and μ_S represent the ordinal scale shift through day 7, 14, and 28 for Ampion and Placebo after randomization. The difference between Ampion and Placebo with respect to the change from baseline at day 7, 14, and 28 will be tested utilizing a Wilcoxon rank-sum test via PROC NPAR1WAY. To assess any potential time trends, an exploratory repeated measures analysis of variance will be performed with terms for treatment, time and the interaction between the two. This will be done utilizing PROC GLM with the REPEATED option.

3.2.2 Change in NEWS2 score from baseline through Day 7, or discharge if earlier.

The hypotheses to be tested are:

$$H_0: \mu_A = \mu_S \text{ versus } H_A: \mu_A \neq \mu_S$$

Where μ_A and μ_S represent the mean change from baseline in the NEWS2 score assessment through day 7 for Ampion and Placebo after randomization. The difference between Ampion and Placebo with respect to the change from baseline at day 7, or discharge if earlier, will be tested utilizing a Wilcoxon rank-sum test via PROC NPAR1WAY. To assess any potential time trends an exploratory repeated measures analysis of variance will be performed with terms for treatment, time and the interaction between the two. This will be done utilizing PROC GLM with the REPEATED option.

3.2.3 Percentage of participants who progress to respiratory failure by Day 28.

The hypotheses to be tested are:

$$H_0: \pi_A = \pi_S \text{ versus } H_A: \pi_A \neq \pi_S$$

Statistical Analysis Plan (SAP) for Clinical Study AP-017

Let π_A and π_S represent the percentage of patients who have respiratory failure for Ampion and control during the first 28 days after randomization.

This difference will be tested utilizing the appropriate chi-square test or Fisher's exact test utilizing PROC FREQ with the EXACT option, if needed.

Also, the median time to respiratory failure will be tested for difference between the two groups via the log-rank test. The log-rank test will be performed using PROC LIFETEST; and the estimation of the time-to-event distributions will be performed using the method of Kaplan and Meier.

3.2.4 Percentage of participants who require Intensive Care Unit (ICU) admission by Day 28; ICU-free days through Day 28; ICU length of stay (LOS) from ICU admission to discharge.

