There are two endpoints in this set. Hypotheses about both will be tested independently. The first hypothesis about the percentage of patients who are admitted to the ICU involves all patients. The second hypothesis involves only patients who are admitted to the ICU. Since it is not known how many many patients will be admitted to the ICU, the testing of the second hypothesis will be considered exploratory and not part of the hierachial testing scheme.

The first hypotheses to be tested is:

$$H_0: \pi_A = \pi_S \text{ versus } H_A: \pi_A \neq \pi_S$$

Where π_A and π_S represent the percentage of patients who are admitted to the ICU for Ampion and Placebo during the first 28 days after randomization. The difference between Ampion and Placebo will be tested via an appropriate chi-square test or Fisher's exact test utilizing PROC FREQ with the EXACT option, if needed.

The second hypothesis to be tested is:

$$H_0: \text{Median}_A = \text{Median}_S \text{ versus } H_A: \text{Median}_A \neq \text{Median}_S$$

Where Median_A and Median_S are the median ICU length of stay for the Ampion and placebo groups. Assuming there is no censoring, this will be tested using the Wilcoxon rank sum test via PROC NPAR1WAY. If censoring occurs, e.g., death, then the log rank test will be used based on PROC LIFETEST.

3.2.5 Modulation of cytokine levels from baseline to Day 5.

The hypotheses to be tested are:

$$H_0: \mu_A = \mu_S \text{ versus } H_A: \mu_A \neq \mu_S$$

Where μ_A and μ_S represent the mean percent change from baseline in the cytokine levels at day 5 for Ampion and Placebo after randomization. The difference between Ampion and Placebo with respect to the percent change from baseline at day 5 will be tested utilizing a two sample t-test via PROC TTEST. To assess any potential time trends an exploratory repeated measures analysis of variance will be performed with terms for treatment, time and the interaction of the two. This will be done utilizing PROC GLM with the REPEATED option.

Statistical Analysis Plan (SAP) for Clinical Study AP-017

3.2.6 Hospital length of stay.

The hypotheses to be tested are:

$$H_0: \text{Median}_A = \text{Median}_S \text{ versus } H_A: \text{Median}_A \neq \text{Median}_S$$

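### The SAP's hierarchy is said to keep alpha without adjustment, but its cytokine step has no passing rule, so strong error control is not assured at that step or for the one after it

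*SAP*

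**What the plan says.** SAP 8.6 (Multiplicity Adjustment) treats the secondary analyses as supportive of the primary and tests them in the order of SAP 3.2: "In order ensure the appropriate alpha level for all tests (without a multiplicity adjustment"). Protocol 9.4.2 agrees: "The secondary endpoints will be tested in a hierarchical manner in the order presented, and thus no adjustment to the alpha level is necessary".

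Two numbered steps in SAP 3.2 can contain more than one test.

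- **SAP 3.2.5, cytokines.** The hypothesis concerns "the mean percent change from baseline in the cytokine levels at day 5 for Ampion and Placebo after randomization", and the difference "with respect to the percent change from baseline at day 5 will be tested utilizing a two sample t-test". The SAP does not say which cytokines. Protocol 5.2 does, with an open list: "A cytokine panel is tested to include, but not limited to: Tumor Necrosis Factor alpha", then interferon gamma and IL-1 beta, then "interleukins (IL-6, IL-8, IL-10, IL-12").
- **SAP 3.2.1, ordinal scale.** The difference "with respect to the change from baseline at day 7, 14, and 28 will be tested utilizing a Wilcoxon rank-sum test". Protocol 9.4.2 lists the three days as separate bullets.

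A third multi-part step, SAP 3.2.4 (intensive care), is resolved: ICU length of stay is declared exploratory and placed outside the hierarchy. Nothing comparable is said for 3.2.5 or 3.2.1. In SAP order, the only step after the cytokines is 3.2.6, hospital length of stay.

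**The concern.** In a fixed sequence every hypothesis can be tested at full alpha because testing stops at the first failure. That argument needs a clear pass or fail at each step. Where a step holds several tests and no rule combines them, pass is undefined. With adjustment ruled out and no rule stated, an analyst could test each analyte at full alpha and count the step as passed if any one is significant.

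Two things are then at stake. A cytokine finding could be reported as alpha-controlled when the chance of at least one false positive in the panel is well above the nominal level. And whether 3.2.6 may be tested at all would depend on that undefined pass. Each single test still has its own error rate of 0.049; what is lost is control over the family, which is what SAP 8.6 claims.

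**Working it through.** **Inputs**

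- Per-test alpha 0.049: SAP 6.1 sets 0.001 for the interim and about 0.049 for the final test, and 0.05 − 0.001 = 0.049. Protocol 9.2.3 gives 0.047, so that value is also shown.
- Number of cytokines: 3 (TNF-alpha, IFN-gamma, IL-1 beta) + 4 (IL-6, IL-8, IL-10, IL-12) = 7, a minimum because the list is open.
- Number of ordinal time points: 3.
- Correlation among tests: not in the documents. Assumed equal for all pairs, with 0 to 0.9 shown.

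The documents state no error rate for the secondary family, so there is no figure of theirs to reproduce on this point.

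**Conditions.** The step is reached, all its null hypotheses are true, and one significant result is enough to pass.

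**Independent tests.** P(at least one false positive) = 1 − (1 − alpha)^k.

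- k = 7: 1 − 0.951^7 = 0.297
- k = 3: 1 − 0.951^3 = 0.140

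**Upper bound for any dependence.** k × alpha: 7 × 0.049 = 0.343, and 3 × 0.049 = 0.147.

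**Correlated tests.** Statistics Z_i = √r·U + √(1 − r)·E_i, with U and E_i independent standard normal; the result is the share of 2 million draws in which the largest |Z_i| exceeds the two-sided 0.049 critical value.

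| Correlation r | 7 cytokines | 3 ordinal days |
|---|---|---|
| 0 (exact) | 29.7% | 14.0% |
| 0.3 | 26.7% | 13.4% |
| 0.5 | 22.5% | 12.3% |
| 0.8 | 14.6% | 9.6% |
| 0.9 | 11.2% | 8.2% |

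At 0.047 per test the independent values are 28.6% and 13.4%, so the conflict between the two final alphas does not change the conclusion.

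**Dependence on the passing rule.** If all seven cytokines had to be significant, a false claim would require a true null to be rejected at 0.049, so the step's error could not exceed 4.9%. The gap between that and the middle column is the effect of the missing rule.

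**Ordinal days.** If Day 7, then Day 14, then Day 28 are separate steps, each is one test, testing stops at the first failure, and the right-hand column does not apply.

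**The case against.** Several parts of the opposing case carry weight.

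- **No any-one-passes rule is written.** SAP 3.2.5 states one null hypothesis and no passing rule. A reader might infer that every analyte is tested at full alpha, that one success suffices, and hence that error control definitely fails. The documents support less: the rule is absent, so control is not assured.
- **The ordinal step is probably sequential.** A reader might count SAP 3.2.1 as an equal failure. Protocol 9.4.2 lists the three days as ordered bullets to be tested in that order, and SAP 3.2.1 keeps the order. This reading protects alpha; the SAP only fails to state it. No such reading rescues the cytokines, for which no order is given.
- **The rates are conditional.** The cytokines are the fifth step in the SAP. If the primary endpoint gates the secondaries, or simply if the first secondary test is a single one, the chance of any false secondary claim when every null is true stays at or below alpha. Inflation arises when earlier effects are real and the step is reached. That limits the problem without removing it, because it is then that secondary claims would be made. SAP 8.6 does not state a gate on the primary.
- **The stakes are modest.** This is a Phase II study, the secondaries are called supportive, and Protocol 5.2 describes the cytokine data as for research purposes. This argues for taking the panel out of the hierarchy. It does not make the alpha claim correct while the panel is in it.

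A reader might also extend the point to the log-rank tests in SAP 3.1 and 3.2.3. The documents give nothing from which their added error could be sized, and the point does not rest on them.

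**Conclusion.** The point holds for the cytokine step. SAP 8.6 and Protocol 9.4.2 claim a property that SAP 3.2.5 does not secure, and the uncertainty carries into 3.2.6. Under the conditions given, the false-positive rate for seven analytes is 29.7% if independent, about 22.5% at correlation 0.5, 14.6% at 0.8 and 11.2% at 0.9, against a nominal 4.9%. A reader might quote the ratio as six-fold (29.7 / 4.9 = 6.1), but that needs seven independent cytokines measured in the same patients; at correlation 0.9 it is 2.3. More analytes than seven would raise the rates.

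For the ordinal scale the finding is only that the sequence should be stated. Without it, three tests in one step could give about 8% to 14%. The primary chi-square or Fisher test is not affected. The change should be made, but the trial's main conclusion does not depend on it.

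**What to change.** 1. In SAP 8.6 and 3.2.5, do one of the following.
   - Declare the cytokine panel exploratory and outside the hierarchy, as SAP 3.2.4 does for ICU length of stay. Step 3.2.6 then follows ICU admission directly. This is the simpler choice.
   - Name the analytes and apply Holm across them (first threshold 0.049 / 7 = 0.0070 for seven). State also what opens 3.2.6: either all named analytes must be rejected, or the cytokine step goes last. Holm within the step does not by itself justify full alpha for 3.2.6 after a single rejection.
2. In SAP 3.2.1, state that Day 7, Day 14 and Day 28 are three consecutive steps in that order, each tested only if the one before is significant. This matches Protocol 9.4.2.
3. In SAP Section 9, record the departure from Protocol 9.4.2, which keeps cytokines in the hierarchy without adjustment and places them before respiratory failure, whereas the SAP places them after ICU admission.

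The cost is a few sentences in SAP 8.6, 3.2.1, 3.2.5 and Section 9. Data collection, sample size and the primary analysis are unchanged. The downside is that cytokine claims become exploratory or slightly harder to reach.

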8.6.1 Post Hoc/Ad Hoc Analyses

Any variables or combinations of variables not described in this plan will be considered post-hoc and identified as such in the CSR. However, all data is being summarized and thus there are no statistical analyses being performed.

9. CHANGES FROM PROTOCOL-SPECIFIED ANALYSES

The statistical analysis of this study has been modified by this amendment to the SAP: The primary endpoint has been amended to assesses the effect of Ampion compared to placebo on prevention of need for mechanical ventilation or death prior to day 28, instead of mortality alone; and, secondary endpoints have been listed in a hierarchical order.

10. LIST OF PLANNED TABLES, FIGURES, AND LISTINGS

Tables are categorized and numbered in accordance with ICH E3 guidelines. Each table, figure and listing is presented by treatment arm. Efficacy tables will be provided for the ITT population and safety tables will be provided for the safety analysis population. Accountability tables will also include an overall column. Listings will be sorted by treatment, subject ID, and by visit, if multiple visits exist.

10.1 Tables

**Statistical Analysis Plan (SAP)
for Clinical Study AP-017**

10.1 Accountability

10.1.1	Accountability (Analysis population: All Enrolled)
10.1.2	Analysis Populations (Analysis population: All Enrolled)
10.1.3	Subject Disposition (All Screened)
10.1.4	Major Protocol Deviations (Analysis population: All Enrolled)
10.1.5	Demographics and Baseline Characteristics (Analysis population: ITT)

10.2 Efficacy (Analysis population: ITT)

10.2.1	Summary of Mechanical Ventilation or Mortality
10.2.2	Summary of Change in Ordinal Scale
10.2.3	Summary of Change in NEWS2 Score
10.2.4	Summary of Progression to Respiratory Failure over Time to Day 28
10.2.5	Summary of ICU admission
10.2.6	Summary of ICU LOS
10.2.7	Summary of Change in Cytokine Levels from baseline to Day 5
10.2.8	Summary of Hospital LOS

10.3 Safety

10.3.1	Overall Summary of Treatment-Emergent Adverse (TEAE) Events
10.3.2	Incidence of TEAEs by System Organ Class and Preferred Term
10.3.3	Incidence of Treatment-Emergent Related AEs by System Organ Class and Preferred Term
10.3.4	Incidence of Treatment-Emergent Serious Adverse Events (SAEs) by System Organ Class and Preferred Term
10.3.5	Incidence of TEAEs by Preferred Term in Descending Order of Frequency
10.3.6	Incidence of Treatment-Emergent Related AEs by Preferred Term in Descending Order of Frequency
10.3.7.1	Summary of Hematology
10.3.7.2	Summary of BioChemistry
10.3.8.1	Summary of Pulse and Change from Baseline over Time (bpm)
10.3.8.2	Summary of Body temperature and Change from Baseline over Time (F)
10.3.8.3	Summary of Systolic BP and Change from Baseline over Time (mmHg)
10.3.8.4	Summary of Diastolic BP and Change from Baseline over Time (mmHg)
10.3.8.5	Summary of respiration rate and Change from Baseline over Time
10.3.9.1	Concomitant Medication Use by ATC Level 1
10.3.9.2	Concomitant Medications Preferred Term in Descending Order of Use
10.3.9.3	Medication Started on Study Preferred Term in Descending Order of Use

Statistical Analysis Plan (SAP) for Clinical Study AP-017

10.2 Listings

Adverse Events

Subject Accountability

1. Randomization List (including, subject ID, randomization number, randomized treatment and treatment administered, and date of treatment)
2. Inclusion and Exclusion Criteria
3. Protocol Deviations
4. Subjects Withdrawing from the Study Prematurely (date and reason)
5. Analysis Populations with Reason for Exclusion (if populations differ)

Demographics and Baseline Characteristics

6. Demographics and Baseline Characteristics
[age, sex, race, ethnicity, weight, height, BMI]
7. Medical History
8. Baseline Medication Use

Efficacy

9. Occurrence of mechanical ventilation or death
10. Ordinal Scale Data
11. NEWS2 score data
12. Progression to respiratory failure by day 28
13. ICU admission and ICU Length of stay
14. Cytokine data
15. Days on ventilation, ventilation free days, date of randomization, date of extubation
16. Hospital length of stay data

Safety

17. All Adverse Events [with indication of TEAE]
18. Hematology Data [with flagging of values outside of normal range]
19. Chemistry Data [with flagging of values outside of normal range]
20. Vital Signs Data [with flagging of values outside of normal range]
21. ECG Data

Statistical Analysis Plan (SAP) for Clinical Study AP-017

10.3 Figures

Note that all figures, unless otherwise stated, will be line plots showing mean \pm SEM at each visit for each treatment arm.

1. Summary of mechanical ventilation and mortality [i.e. Bar Graph]
2. Summary of ordinal scale
3. Summary of NEWS2 score
4. Summary of progression to respiratory failure at day 28
5. Summary of ICU admission and ICU Length of stay (LOS)
6. Summary of cytokine levels
7. Summary of ventilator free days (i.e. Survival curve)
8. Summary of days on ventilation
9. Summary of hospital length of stay (i.e. Survival curve)

